Study design and outcomes

[figure not shown]

Figure 1. Study design and aims

This is a 2-arm pragmatic cluster RCT comparing an enhanced blended learning implementation package to a standard implementation package. The study will be conducted at 34 Tingathe-supported health facilities in Machinga and Balaka, Malawi. Thirty-two of these facility will be considered unique clusters and 2 facilities will be combined to create a 33rd cluster. These 33 clusters will be randomized in a 2:1 ratio to the standard versus enhanced arms. All 33 clusters will receive the standard of care. Additionally, 11 of these clusters will receive an enhanced blended learning training (quarter 0) and enhanced facility support throughout quarters 1-4. Three sets of outcomes will be compared between the standard and enhanced arm over one year: implementation outcomes, service uptake outcomes, and cost-effectiveness outcomes.

For **Aim 1**, the primary outcome is health worker fidelity to ACT counseling procedures.

For **Aim 2**, the ACT cascade will be examined: indexes identified, contacts elicited, HIV self-test kits distributed, contacts tested, and contacts identified as HIV-positive.

For **Aim 3**, we will compare the cost effectiveness between the enhanced and standard implementation arms through cost-effectiveness analyses.

The 22 standard of care sites will receive the enhanced implementation package after the initial cluster RCT period ends. All 33 sites will remain under observation for one additional year. Long-term outcomes will be examined at all 33 clusters through quarter 8 to examine delayed implementation and durability (Figure 2). The main study period will compare all outcomes in A versus B. Additionally, we will examine service uptake outcomes in (A+C+E) compared to (B+D).

[figure not shown]

Figure 2. Study schedule

Prior to implementation of the main trial, the blended learning package and all of the study tools will be pilot tested. The purpose of the pilot test is to examine feasibility and acceptability and refine the tools and implementation package for the trial.

Randomization

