Machinga and Balaka Districts contain 34 facilities. Two small comparable facilities will be combined to create a total of 33 clusters (a number divisible by 3) to achieve 2:1 randomization. The clusters will be classified into strata of sizes 3, 6, or 9 based on key cluster-level characteristics, including district, facility type (hospital, health center, dispensary), and baseline performance (number of indexes identified) to help ensure balance of facility characteristics between the arms. Within each stratum, clusters will be randomly assigned in a 2:1 ratio to the standard or enhanced arms for the cluster RCT period (quarters 1-4). The facilities and their staff will not be blinded to study arm. However, on certain measures, such as audio-recorded fidelity assessments, coders will be blinded to randomization arm. The randomization schedule will be created by an independent statistician using a random number generator in SAS or comparable program.

Evidence based practice

In implementation science, an important first step is clear identification of the evidence-based practice, which in this case is ACT. In the Malawian context, ACT is a voluntary service which consists of offering support to HIV-positive clients to recruit sexual partners and family members for HIV testing. ACT is simple in theory, but complex in practice. Indexes may be adults or children, newly diagnosed or already on treatment. Adult contacts may be

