Recruitment of patients (indexes and contacts) is expected to occur at each facility during the study period. The study team will be assigned to spend time at each facility and will approach potential indexes and contacts about participation in the study. Study team members will be trained in effective communication techniques and will engage the potential participants in brief conversations about the purpose, nature, and duration of the study. If interested, potential participants will be offered the opportunity to provide informed consent, and those who consent will be enrolled.

Procedures

	Pre	Q0	Q1	Q2	Q3	Q4	Q5	Q6	Q7	Q8
Facility survey (FS)		X								
SOC training	X									
Data harmonization		X								
Randomization		X								
Enhanced training Adoption/adherence (AD)		11 clusters					11 clusters	11 clusters		
SOC implementation			X	X	X	X	X	X	X	X
Enhanced implementation			11 Clusters	11 clusters	11 clusters	11 clusters	22 clusters	33 clusters	33 clusters	33 clusters
Service uptake			X	X	X	X	X	X	X	X
HCW consent	X									
HCW surveys	X		X			X				
Simulated fidelity		X	X							
Authentic fidelity			X	X	X	X				
Exit interviews			X	X	X	X				
Time and motion			X	X	X	X				
Focus groups/in-depth interviews	~8 clusters		~8 clusters				~8 clusters			

Facilities will participate in the following procedures:

Pre-trial

- All sites will have standard of care training

Quarter 0

- A facility survey will be conducted
- Data harmonization will occur to ensure all facilities are collecting the same data in the same way.
- All facilities will be randomized to one of the two study arms
- 11 sites randomized to the enhanced arm will receive enhanced blended learning training package

Quarters 1-4

- All ACT procedures will be conducted and service uptake data will be collected
- All clusters will receive standard of care implementation
- 11 clusters will receive enhanced implementation

Quarters 5-8

- All ACT procedures will be conducted and service uptake data will be collected
- 11 clusters randomized to the standard arm will receive enhanced package (Q5)
- 11 clusters randomized to the standard arm will receive enhanced package (Q6)

Health care workers (e.g. HDAs, CHWs, etc.) will participate in the following procedures:

Pre-trial

- At the time of recruitment, health workers will be offered the opportunity to provide informed consent. Those who provide informed consent will complete the remaining study procedures.

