Consistent with implementation science best practices,^{13, 37, 38} we have used an evaluation framework, RE-AIM, to guide analysis.^{93, 94} The five RE-AIM constructs—Reach, Effectiveness, Adoption, Implementation, and Maintenance—align with our research questions. Reach, persons receiving the intervention, will be measured by the rate of potential indexes who are offered ACT. Effectiveness, the ability of an intervention to impact outcomes, will be measured by a range of service uptake outcomes. In addition, positive and negative aspects of index and contact experiences will be measured through exit interviews. Adoption will be measured by the proportion of the enhanced implementation package completed per site. Implementation will be assessed through fidelity assessments, measuring how well health workers adhere to counseling protocols. Maintenance, the degree to which a program becomes part of routine organizational practice, will be examined through the consistency in the other outcomes (effectiveness and implementation) over time. In addition, we expect to explore how the five RE-AIM domains relate to one another (Figure 8).^{83, 84} We hypothesize that adoption of blended learning activities will lead to better implementation and reach which, in turn, will lead to greater ACT effectiveness, and ultimately maintenance (sustainability) over time.

Aim 1 Analytic methods and power calculations (implementation outcomes)

In Aim 1, we will compare the implementation outcomes of the enhanced and standard arms. The primary hypothesis is that fidelity to counseling procedures will be better in the enhanced arm than the standard arm.

Primary outcome of interest (fidelity): The primary implementation outcome of interest is health worker fidelity to ACT counseling procedures. This was selected as the primary implementation outcome because the enhanced training directly targets this outcome. Fidelity will be assessed using a 15-item scale assessing the quality, completeness, and adherence to ACT procedures with raw scores ranging from 0-30 (and recalculated as 0 to 100 percentage points).

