Analyses: Data from quarters 1 through 4 (the cluster RCT design) will be analyzed using a negative binomial mixed-effects model accounting for quarterly repeated measures within each cluster. Models will use a log link, contain terms for randomization arm, and the natural-log transformed number of potential indexes will be incorporated as an offset term. Key baseline variables of interest, such as district, will be adjusted for. Rate ratios and 95% confidence intervals will be used to estimate the effect sizes and quantify the precision of effect estimates for the main analyses which will compare the enhanced versus standard arms for rates of each service uptake outcome per the total number of potential indexes (5 main endpoints denoted above). Secondary endpoints will take the same approach and use a negative binomial mixed effects model as well. Several secondary endpoints are proportion measures; for those endpoints effect size will be measured using a risk ratio and corresponding 95% confidence interval comparing the enhanced versus standard arms. To assess maintenance, interaction terms between quarters and randomization arm will be included to assess whether effects remain constant, intensify, or diminish over time during quarters 1 through 6.

Statistical power assumption, models, and estimates: Sample size calculations were guided by data from the 33 proposed clusters in the two districts from 2019-2020. In these two districts (Machinga and Balaka), Tingatthe supports 34 MOH facilities with implementation of the national HIV program and supervises approximately 150 community health workers and 100 HIV diagnostic assistants. Two nearby facilities in Balaka will be combined for analysis such that the 34 facilities are handled as 33 clusters.

Across these 33 clusters, 4600 persons are diagnosed with HIV each year and another 49,000 are already taking ART. From this, we estimated 35 new HIV-positive diagnoses per cluster per quarter and 372 ART patients per cluster per quarter or approximately 407 total potential indexes per facility per quarter. On average, of these 407 total potential indexes, there were approximately 86 indexes identified (0.21), 97 contacts elicited (0.24), 12 self-test kits distributed (0.03), 25 contacts tested (0.06), and 3 contacts diagnosed as HIV-positive (0.007). These values informed our assumptions for the standard arm.

Power for primary analyses:

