Additional service uptake analyses from the trial (tertiary outcomes)

In addition to the primary analyses described above, rather than using total potential indexes as the statistical offset value, an indicator from the previous step of the cascade will be used. Power calculations were conducted for these secondary endpoints as well. The empirical power approach for rate ratios was described for the primary analysis. For proportion endpoints, a logistic mixed-effects model was used to simulate proportion values between [0, 1], and empirical power to detect a given risk ratio was calculated from a log-binomial mixed-effects model analysis.

		Assumed values for empirical power calculations:							Statistical Power	
Cascade Denominators		Type	Endpoint Rates		Effect size	Expected counts		Nuisance parameters		
Key measures:			Enhanced	Standard	RR	Enhanced	Standard	RIV	Scale	
0. Total potential indexes (TPI)			n/a	n/a	1	407	407			n/a
1. Total indexes (TI)	R	0.3100 per TPI	0.2113 per TPI	1.47	126	86	0.0981	0.0854	85%	
2. Contacts Elicited (CE)	R	1.4200 per TI	1.1279 per TI	1.26	179	97	0.0274	0.0658	83%	
3a. Self-test kits distributed	P	0.2250 per CE	0.1237 per CE	1.82	40	12	0.4260	n/a	83%	
3b. Contacts Tested	P	0.4400 per CE	0.2577 per CE	1.71	79	25	0.5770	n/a	82%	
4. HIV+ Contacts Diagnosed	P	0.0770 per TI	0.0349 per TI	2.21	14	3	0.5681	n/a	81%	

R = Rate; P = Proportion; RR = rate ratio for rates or risk ratio for proportions;
RIV = random intercept variance (i.e., estimated variance of the random intercept for each cluster)
Scale nuisance parameter for the negative binomial mixed-effects model summarizes over-dispersion for rate endpoints
Standard arm counts are per cluster per quarter and calculated by averaging background data from Oct 2019-April 2020 and Sep–Nov 2020
Nominal type I error rate of $\alpha=0.05$ is used throughout, with no adjustment for multiple endpoints

Temporal trend analyses

In addition to analyzing the primary cluster RCT data described above, we will explore temporal trends. Based on Figure 2, we will examine all of the indicators described above, comparing the periods preceding enhanced implementation (B+D) to the periods following enhanced implementation (A+C+E). Period A will also be compared to period C. In these analyses, the analytic procedures described for the primary and secondary analyses will be followed. These models will have terms for the primary exposure of interest and time.

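### The Aim 2 maintenance terms contrast randomized arms through quarter 6, although the standard clusters receive the enhanced package in quarters 5 and 6

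*Combined protocol and SAP*

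**What the plan says.** In the Analyses paragraph of the Aim 2 section, the primary model is a negative binomial mixed model on quarters 1 to 4. The same paragraph adds that, for maintenance, "interaction terms between quarters and randomization arm will be included", in order to assess "whether effects remain constant, intensify, or diminish over time during quarters 1 through 6". It does not mention the rollout, does not recode arm as a time-varying exposure, and does not say whether quarter is linear or categorical.

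Three other sections bear on that window:

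- Randomization assigns the arms for the cluster RCT period, which it defines as quarters 1 to 4.
- Study design and outcomes states: "The 22 standard of care sites will receive the enhanced implementation package after the initial cluster RCT period ends".
- Procedures gives the package to 11 standard clusters in quarter 5 and the other 11 in quarter 6. Its schedule table counts 22 clusters under enhanced implementation in quarter 5 and 33 from quarter 6.

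The Evaluation framework makes Maintenance one of the five RE-AIM constructs, which "will be examined through the consistency in the other outcomes (effectiveness and implementation) over time".

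**The concern.** In quarters 1 to 4 the arm contrast compares clusters with and without the package. In quarter 5 half of the standard clusters are being given it, and in quarter 6 all of them. An arm-by-quarter term that runs to quarter 6 therefore mixes two things: any waning in the enhanced clusters, and any gain in the rolled-out standard clusters. The model cannot separate them.

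The trial's own hypothesis is that the package works. If it does, the later arm ratios shrink and the planned reading is that the effect diminishes, even where it is fully maintained. At stake is the trial's answer on sustainability, which bears on the scale-up that the protocol names as an intended use of the results.

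**Working it through.** **Inputs.** Rates, random intercept variance (RIV) and scale come from the Aim 2 primary power table. There are 11 enhanced and 22 standard clusters and about 407 potential indexes per cluster-quarter. Rollout timing is from Procedures.

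**The plan's own figure first.** With a normal approximation on the log rate, the variance per cluster is RIV + (scale + 1/μ)/4, where μ = 407 × rate. For contacts tested:

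- Enhanced: 0.3340 + (0.2847 + 1/50.8)/4 = 0.410. Standard: 0.3340 + (0.2847 + 1/25.0)/4 = 0.415.
- SE = √(0.410/11 + 0.415/22) = 0.237.
- ln(0.1247/0.0614) = 0.709, so z = 2.99 and two-sided power is 84.8% (stated 85%).

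The other endpoints give 84.5% for indexes (stated 85%), 81.1% for contacts elicited (81%), 83.7% for HIV-positive contacts (82%) and 86.3% for self-test kits (82%). Kits come within 2 points (83.8%) only in a simulation with an assumed cluster-size CV of 0.7 and a t(31) reference. The table's inputs are otherwise adequate for what follows.

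**Expected arm ratio under full maintenance.** Let p be the share of standard clusters already responding. The arm ratio is RR/((1−p) + p·RR) on average rates, or RR^(1−p) on the log scale.

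- Immediate response: p = 0.5 in quarter 5 and 1 in quarter 6.
- One-quarter lag: p = 0 in quarter 5 and 0.5 in quarter 6.

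For contacts tested at p = 0.5: 2.031/(0.5 + 0.5 × 2.031) = 1.34, or √2.031 = 1.43. At p = 1 the ratio is 1.00.

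| Endpoint | RR, quarters 1–4 | RR at p = 0.5 |
|---|---|---|
| Indexes | 1.47 | 1.19–1.21 |
| Contacts elicited | 1.55 | 1.22–1.25 |
| Self-test kits | 2.20 | 1.38–1.48 |
| Contacts tested | 2.03 | 1.34–1.43 |
| HIV-positive contacts | 2.10 | 1.35–1.45 |

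**If quarter is linear.** The least-squares slope over six quarters weights each log ratio by (quarter − 3.5)/17.5. With L = ln RR and L* = the log ratio at p = 0.5, the slope is (−4L + 1.5L*)/17.5 for immediate response and −(L − L*)/7 for lag. For contacts tested on average rates (L = 0.709, L* = 0.293):

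- Immediate: (−2.835 + 0.439)/17.5 = −0.137, a spurious ratio of 0.87 per quarter.
- Lag: −0.416/7 = −0.059, a ratio of 0.94.

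Across endpoints the range is 0.86–0.93 (immediate) and 0.94–0.97 (lag).

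**Simulation with a constant true effect.** 500 trials per endpoint, negative binomial random-intercept model with log offset, Poisson(407) potential indexes in every cluster (an assumption, since cluster-specific means are not given). Monte Carlo error is at most about 4.4 points. The plan states no decision rule for maintenance, so the 0.05 level and 95% CI are used only as a yardstick.

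| Endpoint | Quarter 6 vs 1 term: lag / immediate | 95% CI wholly below 1: no rollout / lag / immediate | Linear interaction rejected: no rollout / lag / immediate |
|---|---|---|---|
| Indexes | 0.81 / 0.68 | 3.6% / 27.0% / 66.4% | 8.0% / 19.0% / 74.8% |
| Elicited | 0.80 / 0.65 | 3.4% / 18.6% / 48.0% | 6.8% / 13.6% / 50.4% |
| Kits | 0.60 / 0.44 | 3.8% / 11.2% / 20.8% | 5.8% / 8.8% / 22.8% |
| Tested | 0.67 / 0.49 | 3.0% / 25.6% / 68.8% | 6.2% / 18.4% / 78.2% |
| HIV-positive | 0.67 / 0.49 | 3.4% / 21.0% / 49.0% | 5.4% / 14.6% / 60.8% |

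With categorical quarter, the quarter 2 to 4 terms stay at 0.98–1.04, so only the quarter 5 and 6 terms are affected. Restricting the linear test to quarters 1 to 4 gives rejection of 4–9%.

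A second model (cluster fixed effects, joint 5-df Wald test, immediate response) rejects in about 70% (indexes), 49% (elicited), 74% (tested) and 51% (HIV-positive), against 4–6% without rollout. For kits that test is miscalibrated (18% without rollout) and is set aside.

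**The case against.** **The window may be leftover wording.** The paragraph opens with quarters 1 to 4, and the section describes datasets of 132 (four quarters) and 264 (eight quarters) observations. A six-quarter dataset would have 33 × 6 = 198, and none is mentioned. That is plausible, but the sentence still sets the window at six quarters and needs the same edit.

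**The plan has exposure-based comparisons.** Temporal trend analyses contrasts periods before and after enhanced implementation, with a time term, and compares period A with C. The fidelity assessments behind the Aim 1 maintenance model are scheduled in quarters 1 to 4. So one supplementary Aim 2 assessment is affected, not the whole Maintenance construct. This stands. But those comparisons do not change the arm-by-quarter rule, and the two could give conflicting answers.

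**The size rests on assumptions.** This also stands. The largest rejection rates need every rolled-out cluster to reach the full effect in the quarter it is trained, so they are best read as an upper bound. Under a lag the inflation is modest, and for kits 8.8% against 5.8% on the linear test is not a clear inflation. The simulated kits ratio under lag (0.60) is also slightly below its analytic range of 0.62–0.67 (1.376/2.203 to 1.484/2.203).

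**Quarter 5 may hold usable information.** Eleven standard clusters are still without the package then, and under a full one-quarter lag the quarter 5 contrast is undistorted. That is fair, but the lag is not known in advance, and the plan's term uses all 22 standard clusters as the comparator.

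**Conclusion.** The concern holds. As written, the maintenance terms can report a diminishing effect when the effect is fully maintained. For contacts tested, the quarter 6 arm ratio would be 1.00 (immediate response) or 1.34–1.43 (one-quarter lag) in place of 2.03. Across endpoints, the quarter 6 versus quarter 1 term would be 0.44–0.68 or 0.60–0.81 in place of 1.

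These figures assume a constant true effect, the same rate ratio in rolled-out clusters, the power-table parameters, and the rollout timing in Procedures. The timeline under Work plan and Timeline, as extracted, marks delayed rollout in Year 2 quarters 2–3. That may be earlier than quarters 5–6 or an extraction artefact, and it is not relied on.

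The direction of the bias does not depend on the parameter values, only on rolled-out clusters gaining something. The primary comparison and its power are untouched. The assessment is supplementary and no power is claimed for it, so this should be corrected but does not threaten the main result.

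**What to change.** In the Aim 2 maintenance sentence, end the window at quarter 4 and state whether quarter enters as a linear or a categorical term. Add a pointer to Temporal trend analyses for durability in quarters 5 to 8, where the models use exposure rather than arm and include time. Note there that, on the Procedures schedule, no concurrent unexposed clusters remain from quarter 6, so separating exposure from calendar time then depends on the model.

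The cost is one or two sentences of SAP wording and no new data. The arm-based maintenance assessment covers four quarters instead of six. What is given up is quarter 6, which has no unexposed comparator, and quarter 5, which is clean only if rolled-out clusters have not yet responded. If the investigators want to use quarter 5, a time-varying exposure or time-since-rollout term is the alternative to the randomized-arm term.

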Aim 3 Analytic methods (Cost-effectiveness)

In Aim 3, we will explore the budget impact and cost-effectiveness of the enhanced and standard approaches. Our modeling will allow us to examine the inherent tradeoffs of the high upfront and ongoing expenditures of the enhanced package with the anticipated future health benefits, such as earlier linkage to care and averted illness that are known to be realized with more effective contact tracing and testing. All analytic decisions will be guided by best practices in implementation economics, a rapidly evolving field.

Cost measurement: We will embed an empirical costing study in our trial. Costs will be collected in two ways: micro-costing and time-motion logs (self-reported and directly observed). Micro-costing will be used to quantify resources associated with the development and implementation of the entire enhanced package. This includes costs of blended learning development, tablets, HIV tests and supplies, travel and telecommunications for tracing, and training expenses. Cost data will be available through contractual information with developers, receipts, and MOH supply chain partners. We will also extract data from project expenditure and management records, including purchase logs and human resources records (e.g. health worker rota), where appropriate. Time-motion assessments in both arms will record staff time and effort on ACT tasks, allowing us to reliably apportion effort expended on ACT activities. This includes health worker and facilitator time spent with the blended learning package and time spent counseling indexes, tracing contacts, and supporting contacts with HIV prevention or treatment services. Data for time-motion logs will be collected by observing staff in each cluster approximately two times. Our research team has conducted these assessments previously. They will be conducted in line with the STAMP checklist (Suggested Time and Motion Procedures).⁹⁰⁻⁹² Additionally, on the provider survey, health care workers will report estimated time spent on these activities.

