We will record this information in structured spreadsheets that document each resource, category, quantity, and unit cost. This comprehensive costing will follow international conventions for costing (i.e. including items for staff, equipment, consumables, and any overhead that are not common to both arms); discounting future costs; and reporting based on accepted practices⁹³ and guidelines from the Panel on Cost-Effectiveness in Health and Medicine.⁹⁴ We will not include any costs related to study-specific activities (e.g. data collection).

We will first conduct a budget impact analysis, comparing total costs associated with the development and implementation of the enhanced implementation strategy to the standard strategy to provide affordability information.⁹⁵⁻⁹⁷ This will be conducted from the perspective of the health-system, evaluating programmatic costs at a per facility basis. We will initially examine only facilities under observation, but ultimately extrapolate the model to 750 sites that make up Malawi's national HIV program.⁹⁸ Due to up-front costs of developing the capacity-building blended learning tool, as the scale and duration of implementation increases and expands, we expect that the cost per facility will decrease.

Cost effectiveness modeling: We will conduct cost-effectiveness analysis, modeling incremental cost effectiveness ratios (ICERs) per contact tested and per HIV-positive patient diagnosed. We may also examine incremental cost per HIV infection averted and per disability adjusted life year (DALY) averted comparing the enhanced to the standard approach. We will construct a hybrid decision-tree/Markov model to reflect the relevant programmatic components and clinical outcomes based on ACT implementation as described above and a literature review of key parameters. This model will first be limited to the trial population, estimating approximately 50,000 total potential index patients in these 33 clusters over one year, and then expanded to the national program—estimating approximately 800,000 potential annual indexes over one, three, and five years. Imbedded Markov models will

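### The national budget impact is offered as a health-system affordability result but stops at development and implementation costs, leaving out treatment and care for the additional contacts diagnosed

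*Combined protocol and SAP*

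**What the plan says.** Under Aim 3 Analytic methods (Cost-effectiveness), the first analysis is a budget impact, "comparing total costs associated with the development and implementation of the enhanced implementation strategy to the standard strategy to provide affordability information". Its viewpoint is set in the next sentence: "This will be conducted from the perspective of the health-system, evaluating programmatic costs at a per facility basis". It starts with the facilities under observation and is then extended to the 750 sites of the national HIV programme. The plan expects cost per facility to decline as scale and duration grow, because the development cost is spread more widely.

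Under Cost measurement, the scope is again the package: "Micro-costing will be used to quantify resources associated with the development and implementation of the entire enhanced package". The items follow: "This includes costs of blended learning development, tablets, HIV tests and supplies, travel and telecommunications for tracing, and training expenses". Time-and-motion work adds staff effort, including "time spent counseling indexes, tracing contacts, and supporting contacts with HIV prevention or treatment services". That staff time is the only treatment-related item in Aim 3. Antiretroviral drugs, laboratory monitoring and continuing clinic care are not named.

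The general costing convention is broader: "including items for staff, equipment, consumables, and any overhead that are not common to both arms); discounting future costs". The committed cost-effectiveness ratios are per contact tested and per HIV-positive patient diagnosed. Two further ratios are optional: "We may also examine incremental cost per HIV infection averted and per disability adjusted life year (DALY) averted".

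**The concern.** A health-system payer asking whether national roll-out is affordable has to fund two things: the package, and care for the people it finds. The trial is powered for roughly a doubling of HIV-positive contacts diagnosed, so the second item is an intended consequence of success. The budget impact as defined contains only the first.

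The two items also move differently over time. Development cost is spent once and shrinks per facility as sites are added. Treatment is a recurring cost that builds with each year's diagnoses. A ministry reading the planned result would see a falling cost per facility and would not see the rising item beside it. The plan's own convention of counting items that differ between arms points towards including that item, because care for the additional diagnoses is not common to both strategies. The budget impact definition is narrower than that convention.

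**Working it through.** **Inputs from the documents**
- HIV-positive contacts diagnosed per potential index: 0.0155 enhanced, 0.0074 standard (Aim 2, table under Power for primary analyses).
- Potential indexes: 407 per cluster per quarter (Aim 2); about 800,000 a year nationally, with horizons of one, three and five years (Aim 3).
- National sites: 750 (Aim 3).
- Share of HIV-aware adults on treatment: 91% (Study Setting), used only as a proxy for linkage.

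**Step 1: reproduce the plan's figures for this endpoint.**
- Rate ratio: 0.0155 / 0.0074 = 2.095 (stated 2.10).
- Expected counts: 407 × 0.0155 = 6.3 and 407 × 0.0074 = 3.0 (stated 6 and 3).
- Power, by a Wald approximation on the log rate ratio with per-cluster variance = 0.3334 + (1/mean + 0.3039)/4, 11 versus 22 clusters, two-sided 0.05 assumed: 83.7% with normal quantiles, 81.3% with t on 31 degrees of freedom (stated 82%).

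The rates are therefore the ones the trial is built on.

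**Step 2: extra diagnoses a year nationally.**
- Enhanced: 800,000 × 0.0155 = 12,400.
- Standard: 800,000 × 0.0074 = 5,920.
- Difference: 800,000 × 0.0081 = 6,480.

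**Step 3: treatment person-years.** Each year adds 6,480 people who start mid-year, all are treated, and none leave care. Cumulative person-years = 6,480 × (0.5 + 1.5 + … ), one term per year.

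| Horizon | Sum of terms | All treated | 91% treated |
|---|---|---|---|
| 1 year | 0.5 | 3,240 | 2,948 |
| 3 years | 4.5 | 29,160 | 26,536 |
| 5 years | 12.5 | 81,000 | 73,710 |

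**Step 4: the trend per site.** Person-years within year 1 are 6,480 × 0.5 = 3,240, or 3,240 / 750 = 4.3 per site. Within year 5 they are 6,480 × 4.5 = 29,160, or 29,160 / 750 = 38.9 per site. The omitted item grows ninefold (4.5 / 0.5) over the period in which the plan expects cost per facility to fall.

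**Step 5: money, by assumption only.** No treatment unit cost is in the documents. At an assumed US$50 to US$300 per person-year, 81,000 person-years cost US$4.05 million to US$24.3 million undiscounted, or US$5,400 to US$32,400 per site over five years. No package cost is given either, so the share of the total budget cannot be worked out.

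**The case against.** The strongest reply is that the budget impact declares its scope openly. It concerns programmatic costs per facility, and a delivery-only budget is a legitimate product. That stands as far as it goes: the planned figure is worth reporting. It does not justify presenting that figure alone as national affordability from the health-system perspective.

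The size is also open to challenge. The rates are a powered effect, not a forecast. They are applied here to all 800,000 potential indexes from the first year and held constant for five. Attrition, death, depletion of undiagnosed contacts and discounting are ignored. The plan itself speaks of earlier linkage, so some of these contacts would be diagnosed later under the standard strategy, and their treatment is not wholly incremental. Savings from infections averted are not netted off. All of this stands, which is why 81,000 is an upper figure. None of it removes the gap.

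A reader might go further and infer that cost per DALY or per infection averted would credit the benefit of treatment without paying for it, since the plan speaks of weighing "tradeoffs of the high upfront and ongoing expenditures of the enhanced package with the anticipated future health benefits". The documents do not support that. The itemised list describes what the trial's costing study will collect, and is not the input list of the Markov model. That model follows HIV-positive contacts through health states, draws on a literature review for key parameters, and sits under a convention that discounts future costs and counts items differing between arms. Treatment cost could enter there; the plan neither includes nor excludes it. Those two ratios are also optional.

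**Conclusion.** The point holds for the budget impact. As written, it understates what the health system would pay if the package works as powered, because treatment and care for additional HIV-positive contacts are outside its definition. The fault is an understated cost: the budget impact credits no health benefit, so nothing is being claimed there without payment.

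The scale is about 6,480 extra diagnoses a year nationally and at most about 81,000 treatment person-years over five years. This assumes the powered rates hold constantly at national scale, full linkage, mid-year starts, no attrition, and no later diagnosis under the standard strategy. The dollar range rests on an assumed unit cost and is illustrative only.

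For the optional ratios per DALY and per infection averted, the finding is one of missing detail: the plan should say whether treatment costs enter. No bias in those ratios is shown. The two committed ratios are unaffected.

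**What to change.** Report the budget impact on two lines.

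1. **Package only**, as planned, labelled programme-delivery cost.
2. **Package plus treatment and care** for HIV-positive contacts, adult and paediatric, under both strategies. Where infections averted are modelled, net off the treatment they save; otherwise state that the line is gross.

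Take unit costs for drugs, monitoring and visits from the MOH supply chain partners already named as a cost source, or from the planned literature review. State the horizon, and vary the unit costs and linkage in the one-way and probabilistic sensitivity analyses already planned. If the ratios per DALY or per infection averted are run, attach the same costs to the HIV-positive health states in both strategies and say so in the plan.

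The cost is a revision to the Aim 3 text and a few more sourced inputs, with no change to trial conduct. The affordability figure on the second line will look less favourable; the planned result is kept on the first.
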